Wherever possible, this retinoscopy result will be modified subjectively with the patient reading letters or symbols presented on the test chart through different lenses selected by the optometrist in order to refine the retinoscopy result. The patient's Visual Acuity with the final spectacle prescription found by retinoscopy or subjective examination will be recorded. It is estimated that retinoscopy will be possible on 70% of our patients, with subjective refinement possible in most of these (50% of the total sample). These results will contribute to the identification of uncorrected refractive error and visual impairment.

7. Posterior eye examination: At this stage in the test the patient's pupils will normally be dilated using tropicamide eye drops to facilitate the examination of the eye's structures behind the iris, notably the lens, the retina and other back of the eye structures. Prior to pupillary dilation, the likelihood of the pupil dilation provoking an acute angle closure glaucoma (ACG) attack will be assessed using the pen light test for anterior chamber depth estimation (Elliott 2007). The risk of provoking an acute ACG attack with tropicamide is very low (Pandit and Taylor 2000, report zero cases of ACG in almost 4000 dilations). However, patients judged at risk of an ACG attack will not be dilated and will be examined through undilated pupils.

The tropicamide drops take approximately 15 - 20 minutes to produce a sufficiently dilated pupil. During this time the patient can have a break, if required, the examiner can complete the MMSE if necessary, the strength of any current glasses can be measured using a focimeter, and the external eyes can be examined using the ophthalmoscope. Once the pupils are fully dilated the examination of each eye follows using a direct hand held ophthalmoscope. The patient needs only to keep their eyes open and, if possible, to follow instructions as to where to direct their gaze. It is estimated that direct ophthalmoscopy will be possible on 85% of our patients and the results will contribute to the identification of cataract, AMD, diabetic retinopathy and glaucoma suspects.

As a further check on the possibility of a dilation-induced acute ACG attack, post-dilation IOPs will be measured using the iCare tonometer. A significant increase in IOP could be an indicator of a pending ACG attack and if this is suspected the optometrist will remain for a further hour and continue to monitor the patient.

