8. Visual fields: If possible the patient's central visual fields will be plotted. This is by far the most demanding of the tests attempted in this eye examination and will not be possible in many of the patients. The visual field test used will be a supra-threshold test (faster and less confusing than threshold testing) using the Oculus Easyfield, or FDT (Frequency Doubling Technology) or equivalent perimeter. It is estimated that visual field testing will be possible on only 20% of our patients. The results will contribute to the identification of glaucoma suspects.

9. Quality of Life: In cases where visual impairment has been detected or treatable conditions have been undetected or untreated we will measure the patient's quality of life using an

established tool (VISQOL, EQ-5D or QoL-AD) and ask our experts on the Steering Group (ophthalmologist and old age psychiatrist) to offer a clinical view which will be added to the data and included in the study analysis.

10. Conclusion: The examination will conclude with verbal and written advice being passed on to patient and/or carer. This will include advice on any referral required, on the use of new spectacles, and on the recommended date of the patient's next eye examination. The carer and/or patient will be given a leaflet explaining the effects of the tropicamide drops, including the symptoms and signs of an ACG attack and advice on the action to take in the unlikely event of this occurring.

If patient cooperation is poor the optometrist will move step 7 forward in the eye examination. This will allow the optometrist to focus on ophthalmoscopy through dilated pupils, which is the key test for detection of eye disease and which does not require much patient co-operation. Carer's views will be sought on the extent to which the subject's ability to cooperate with the examination reflected his or her usual state. This will be noted on the record card.

Based on their experience with the patient, the optometrist will record how accurate the results from each patient are likely to be.

Participating optometrists will receive training to ensure an optimal standardised approach to examination. This pre-study training will include guidance on the ethical issues associated with research on subjects with dementia.

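### When cooperation is poor, the dilating drops may be given before tonometry, leaving the post-dilation check for a rise in IOP without a baseline

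*Protocol*

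**What the plan says.** All references are to the Protocol, Data collection, Stage 1, unless stated otherwise.

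- **Usual order.** Item 5 is iCare tonometry, item 6 is retinoscopy, and item 7 is the posterior eye examination, which normally starts with tropicamide. The text before item 1 lets the optometrist change the order or leave tests out to suit the patient.
- **Before the drops.** Item 7 requires a pen light estimate of anterior chamber depth, and "patients judged at risk of an ACG attack will not be dilated". It calls the risk of an acute angle closure glaucoma (ACG) attack very low and cites a review said to "report zero cases of ACG in almost 4000 dilations".
- **After the drops.** "As a further check on the possibility of a dilation-induced acute ACG attack, post-dilation IOPs will be measured using the iCare tonometer". The reason given is that "A significant increase in IOP could be an indicator of a pending ACG attack". Where the optometrist suspects one, the response is to stay on for another hour of observation. No absolute IOP level is stated.
- **Exception.** After item 10: "If patient cooperation is poor the optometrist will move step 7 forward in the eye examination". The stated purpose is to concentrate on ophthalmoscopy through dilated pupils, described as the key test for eye disease.
- **Records and advice.** Also after item 10, "the optometrist will record how accurate the results from each patient are likely to be". Under item 10 a leaflet is given, "including the symptoms and signs of an ACG attack and advice on the action to take".

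**The concern.** The post-dilation check is worded as a change, and a change needs two readings. The usual order supplies the first at step 5. The poor-cooperation rule moves the whole of step 7, drops included, and can place it ahead of step 5. One stated rule can then remove the comparison on which another stated check relies.

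Two things are at stake. First, the optometrist may have only a post-drop IOP when deciding whether to stay for the extra hour of monitoring. Second, item 5 uses IOP to help identify glaucoma suspects and ocular hypertensives. In the altered order the only IOP is a post-drop value, and the protocol does not ask for it to be marked as such; the accuracy note is a general one for each patient.

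**Working it through.** The protocol gives no figure to reproduce. The check is of sequence, with one small calculation for scale.

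**Step 1: what moves.** Tropicamide is part of item 7, so moving step 7 moves the drops. The pen light screen is also in item 7 and moves with it.

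**Step 2: what could hold tonometry in place.** Items 1 to 10 and the text around them were read for any rule that IOP must be measured before the drops. There is none. The pen light test is the only check required before dilation, and it is not an IOP reading. Item 7 lists activities for the 15 to 20 minute wait after the drops, and tonometry is not among them.

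**Step 3: the possible orders for a dilated participant.**

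| Order | IOP before drops? | Can a rise be seen? |
|---|---|---|
| 5, 6, 7 (usual) | Yes, if tonometry succeeds | Yes |
| 5, 7, 6 (step 7 passes step 6 only) | Yes, if tonometry succeeds | Yes |
| 7 before 5 | None planned | No |

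The rule permits both the second and third rows and does not choose between them. A participant left undilated after the pen light test is unaffected.

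**Step 4: how many.** The count would be

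N × (share with poor cooperation) × (share of those where step 7 passes step 5) × (share of those dilated) × (share of those in whom tonometry before the drops would have succeeded).

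N is 2 × 385 = 770. The protocol gives none of the four shares. Its 90% feasibility for tonometry is a whole-sample estimate, not one for poor cooperators. The count therefore cannot be derived, and it is zero if optometrists only ever move step 7 past step 6.

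**Step 5: missing baselines that do not come from this rule.** At 90% feasibility, 100% − 90% = 10% have no tonometry in any order, or 0.10 × 770 = 77 people if all 770 are examined. Some of the participants for whom step 7 is moved may be among them.

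**Step 6: safety scale.** Take almost 4000 as 4000. With 0 attacks in 4000 dilations, the one-sided 95% upper limit is

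1 − 0.05^(1/4000) = 0.00075, about 0.075% per dilation.

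The observed rate is zero. The limit is a bound for dilation in general, assumes the same risk in this population, and does not measure the effect of a missing baseline.

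**The case against.** The strongest reply is that the rule is a deliberate trade-off. In participants who may stop cooperating at any moment, it secures the examination that matters most for prevalence. Tonometry touches the cornea and needs open eyes and reasonably steady fixation, so putting it first partly reverses that choice to protect a secondary check. This stands as a reason to make the attempt optional. It does not remove the gap: item 5 describes the instrument as well accepted with no need for anaesthetic, and item 7 already asks for the same test on the same dilated participant soon afterwards.

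The reply continues that the check is an additional one and that action follows clinical suspicion, with no fixed numerical trigger, so an optometrist can still act on a plainly high pressure. That also stands. The check is weakened in this order, not lost.

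Optometrist training and the data collection forms, which the timetable lists as a separate task, are not shown and may already cover the sequence. Nor is a missing baseline peculiar to this rule, as the 10% without feasible tonometry shows.

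A reader might infer that every poor cooperator loses the baseline. The text does not support this, because moving step 7 past step 6 alone keeps it. A reader might also infer biased glaucoma prevalence. That is not supported either: IOP is one input beside ophthalmoscopy and visual fields, the Data analysis section does not list ocular hypertension among its prevalence outcomes, and the protocol gives no effect of the drops on IOP.

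**Conclusion.** The point holds in a limited form. As written, the poor-cooperation rule can put tropicamide ahead of the only planned pre-drop IOP, and in dilated participants where it does, the planned measurements cannot show a rise. This rests on the protocol's wording alone; training material or record forms could close the gap.

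The size is unknown and may be zero. The safety effect is modest, given the pen light screen, the exclusion of at-risk patients from dilation, the leaflet and the low stated risk. It would be wrong to multiply the 0.075% bound by the sample size and read the product as attacks to be expected, since the observed rate is zero and the bound says nothing specific about this gap. No prevalence bias is shown. This is a cheap improvement, not a flaw that threatens the study.

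**What to change.** Add to the paragraph after item 10: when step 7 is moved forward, iCare tonometry is attempted before the drops where the participant accepts it, and is not pursued if they decline that test. State that signs of distress or unwillingness to continue remain governed by the existing rule (Protocol, Including patients who lack capacity), under which the assessment stops and the participant is withdrawn. The new sentence must not suggest that tonometry can be skipped and the examination continued once distress shows.

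Record for each IOP whether it was taken before or after the drops. Where there is no pre-drop reading, judge the post-dilation check on an absolute IOP level agreed beforehand with the Steering Group ophthalmologist. That level also serves participants who have no baseline for other reasons.

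The cost is a short addition to the procedure, a before/after box on the record card, a line in optometrist training and one agreed IOP level. The downside is that a brief corneal-contact test precedes the key examination in the least cooperative participants, and some will still have no baseline.

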PROTOCOL V2 (Current from: 13.12.2012) Detailed Project Description submitted to NIHR

Full title of project: The prevalence of visual impairment in people with dementia

Aims and objectives

The risks of developing both dementia and visual impairment (VI) increase with age, so a large population of people in the UK affected by dementia may also have VI. Demographic research predicts an ageing UK population resulting in increasing prevalences of dementia and the major causes of VI. A brief review of literature on VI and dementia revealed inconclusive prevalence data due to methodological differences in subjects' age, research setting (care home residents and non residents) and definitions of VI. Furthermore, much of the research is 10-30 years old and few studies were UK based. This led to identification of the main research question which is: What is the prevalence of a range of vision problems in people with dementia aged 60-89 years and to what extent are these conditions undetected or inappropriately managed?

The objectives are:

- 1. To measure the prevalence of a range of vision problems in people with dementia.
- 2. To compare the prevalences found in Objective 1 with the published data on the general population in a comparable age range.
- 3. To identify and describe reasons for any under detection or inappropriate management of visual impairment in people with dementia.
- 4. To recommend interventions to improve eye care for people with dementia and further research in this area.

Background

The risks of dementia and visual impairment (VI) both increase with age so it is probable that a large proportion of people with dementia may also have VI. UK demographic changes suggest that ever-increasing numbers of people will be affected by both conditions. However, good quality prevalence data on the topic are lacking.

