It is estimated that between 20% and 50% of older people have undetected reduced vision (10) and it is likely that there is significant under-detection and inappropriate management of VI in people with dementia (14, 15, 16). We have run pilot focus groups with optometrists, family members of people with dementia and professional carers, and our results support these findings. More information is needed on VI prevalence in people with dementia, particularly the extent to which problems may be undetected or inadequately managed and the reasons why. This is particularly significant because VI can contribute to other problems (17). Older people with VI are almost twice as likely to have a fall (18) and behavioural and psychological problems in people with dementia can also be exacerbated by poor vision (10). Loss of vision profoundly affects quality of life (10, 19) and increases the relative risk of admission to care homes (3.3 compared to people who are visually intact)(22). Conversely, cognitive impairment improvements have been reported after cataract surgery (20, 21). In summary, clarification on visual deficits in dementia patients is needed more than ever (23).

Need

Health need: Many cases of visual impairment (VI) in elderly people can be either prevented or successfully treated. However, without early detection and correct management some

conditions can lead to blindness. Evans et al (10) concluded that there is overwhelming evidence that a very large proportion of older people do not receive appropriate eye care and that the sight of many of these people could be improved.

Furthermore, behavioural and psychological problems in people with dementia are reduced when VI is prevented or corrected, with a corresponding positive impact on quality of life.

This study will measure the prevalence of visual impairment in older people with dementia, assess whether or not it is higher than in the elderly population in general and identify the proportion of cases that are undetected. Moreover, the qualitative element of the study will employ multiple perspectives to explain why vision problems go undetected in people with dementia, inform practice and lay foundations for further research to address this issue. Increasing the awareness of the need for appropriate eye care among people with dementia, carers and eye care professionals will help to improve equity of care.

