The Stage 1 cross sectional study will investigate two groups of people with dementia aged 60-89 years with 385 people in each group. Group 1 will comprise people living at home and Group 2 will comprise people living in care homes. The sample size has been calculated to allow detection of a prevalence of 50% with 5% precision and 95% confidence based on the reported estimated prevalence of VI in the population (5, 26). Subjects will be recruited through Memory Clinics and Old Age Psychiatry clinics in NHS trusts and through general medical practices with the assistance of DeNDRoN and Local Coordinating Research Networks. Additionally, Group 1 subjects will be recruited through Alzheimers Society local groups and Group 2 subjects will be recruited through direct contact with care homes. Where participants are recruited via AS, they will only be recruited from groups of service users for whom a medical diagnosis of dementia has been confirmed through the AS processes. It should also be noted that recruitment through AS is not intended to be the primary route, but rather an additional source of participants to enhance the overall recruitment strategy. BUPA

has offered to support the study but we will also recruit through other care providers to reduce the risk of selection bias. Further subjects for both groups, especially those living at home, can also be recruited through The Outside Clinic, one of the UK's leading providers of domiciliary eye care services. They have informed us that they test approximately 2,500 people with dementia each year (living in their own homes and in care homes).

Strategy: The team is aware that recruitment of people with dementia into research studies is not easy and we have adopted a multilayered approach to recruitment. It is intended that the majority of subjects for the prevalence study will be recruited with the assistance of regional DeNDRoNs and CLRNs.

DeNDRoN is launching the ENRICH research ready-care home network this year and we will make use of this to recruit participants.

Identification procedures

Potential participants with dementia will be identified from their medical records by the direct care team or by DeNDRoN or Local Coordinating Research staff who are frequently embedded in NHS clinics. In addition DeNDRoN maintain case registers of patients with dementia who are willing to participate in research and suitable participants who are on this register will be identified and approached.

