Stage 2: Data will be collected from focus groups of eye care professionals, family carers and professional (paid) carers and interviews with people with dementia. The focus group question schedule will be semi structured and cover participants' understanding of eye care for people with dementia; expectations of the eye examination; experience of eye examination and eye care of people with dementia; barriers encountered; and facilitators and strategies to improve eye care. Data obtained in each interview will depend on the individual's ability to recall, communicate and comprehend and will vary according to the degree of dementia.

Data analysis

Stage 1 – prevalence, along with their 95% confidence intervals, of VI due to refractive error, cataract, age-related macular degeneration, glaucoma and diabetic retinopathy will be established. These Confidence Intervals will be used to compare the prevalence of the VIs with published figures in the general population. Prevalence levels between people living at home and people living in care homes will be compared using tests for two independent proportions. Proportions of both previously undetected cases and detected but inappropriately managed cases will also be compared between people living at home and in care homes.

Missing data:

Our primary research objective was to measure the prevalence of a range of vision problems in a generic sample of people with dementia aged 60 to 89 years. The study is adequately powered to achieve this objective. The use of two groups of subjects is mainly to allow us to identify any differences in the level of undetected or inappropriately managed visual impairment between the two groups. This will inform Stage 2 of our study, in which we will investigate the reasons for any undetected or inappropriately managed visual impairment.

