Our sample size of 385 subjects in each group is based on an estimated prevalence of 50% with 5% precision and 95% confidence. This figure of 50% was the highest prevalence quoted in the literature for one of our target conditions. If the prevalence of a condition is either greater than or less than 50% then the study will require a sample size smaller than 385. We had anticipated that in a study of this nature there would be some missing data for each of the optometric tests as some of the participants/patients will be unable to perform them. There is no published data on the percentage of those with dementia who will be able to perform successfully individual elements of an eye examination. In the absence of published data we

took the view when writing our proposal that even if as few as 50% of subjects were able to complete a particular test with a prevalence of 50% (the worst case analysis) we would still have data from 385 subjects (50% of our total of 770), which is sufficient to generate a reliable estimate of the overall prevalence for the condition in a generic sample of patients with dementia.

Following the request for more detail on the impact of missing data we have consulted with a number of optometrists with extensive experience of eye examinations conducted on patients with dementia. Based on their responses we have quoted in Section 2 above (Testing people with dementia) estimates for the percentage of patients with dementia who are likely to be able to complete each test. The lowest percentage they estimate is 60%, compared with our worst case figure of 50% which was the figure used for our sample size calculation. Furthermore, these estimates suggest that, not only does our study have sufficient power to be able to generate a reliable generic figure for prevalence in dementia for each of our target conditions, but also that we should have sample sizes that are sufficiently large to allow statistical testing of differences in prevalence between our two groups (care home residents versus those living at home) for at least two thirds of the target conditions.

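### Objective 2 sets published prevalence figures against the study's own 95% intervals alone, which leaves out the published figures' sampling error and flags chance differences more often than the nominal rate

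*Protocol*

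**What the plan says.** Objective 2, under Aims and objectives, is "To compare the prevalences found in Objective 1 with the published data on the general population in a comparable age range". The Need section gives the direction of interest: the study will "assess whether or not it is higher than in the elderly population in general".

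The method is in the Stage 1 part of Data analysis. The study will establish "prevalence, along with their 95% confidence intervals, of VI due to refractive error" and to cataract, age-related macular degeneration, glaucoma and diabetic retinopathy. It continues: "These Confidence Intervals will be used to compare the prevalence of the VIs with published figures in the general population". The sentence after that assigns tests for two independent proportions to the comparison of home with care home residents, and to nothing else.

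Sampling plans "two groups of people with dementia aged 60-89 years with 385 people in each group", so 770 in total. Background quotes general-population figures for visual impairment of 14.3%, 30% and 50.5%, and 3.3% for glaucoma in the over-70s. It gives no sample size or interval for any of them.

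**The concern.** Objective 2 asks whether two populations differ, and both prevalences are estimated from samples. The study's interval carries the sampling error of this study only. Set against a published figure, it can show whether prevalence in dementia is compatible with exactly 14.3%, say. It cannot show by itself whether prevalence differs from the general-population value that 14.3% estimates, because that estimate has error too.

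The protocol uses a two-sample method where both samples are its own and a one-sample interval where the second estimate is published. Followed as written, the plan can report visual impairment as more common in dementia when the gap is within the combined sampling error of the two sources. The comparison is one of four objectives, and the findings are meant to feed professional guidelines and training.

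**Working it through.** **Inputs from the protocol.** 95% intervals (two-sided 5%, so 2.5% in the 'higher' direction); 385 per group and 770 in total; expected completion of 60% for visual acuity (0.60 × 770 = 462); published prevalences of 3.3%, 14.3%, 30% and 50.5%.

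**Assumed.** The size *m* of the published survey, varied because the protocol does not state it. Both sources are treated as simple binomial samples.

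**Step 1: the plan's own figure.** Sampling states: "The sample size has been calculated to allow detection of a prevalence of 50% with 5% precision and 95% confidence". For one proportion, n = 1.96² × 0.5 × 0.5 / 0.05² = 384.2, rounded up to 385. This reproduces. It is a precision calculation for a single prevalence and does not cover a comparison with an external estimate.

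**Step 2: error of the comparison as written.** Let the true prevalence p be the same in both populations, with *n* evaluable study participants. The study interval has half-width 1.96 × √[p(1−p)/n]. The gap between the two estimates has standard error √[p(1−p)/n + p(1−p)/m]. The interval therefore excludes the published figure with probability

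2 × {1 − Φ(1.96 / √(1 + n/m))},

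and p cancels. Example: n = 770, m = 1,000 gives √1.77 = 1.330, then 1.96/1.330 = 1.473, and a two-sided error of 14.1%. Half of that, 7.0%, is in the 'higher' direction.

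| Survey size *m* (assumed) | n = 385: two-sided / 'higher' | n = 462 | n = 770 |
|---|---|---|---|
| 500 | 14.1% / 7.0% | 15.8% / 7.9% | 21.9% / 10.9% |
| 1,000 | 9.6% / 4.8% | 10.5% / 5.3% | 14.1% / 7.0% |
| 5,000 | 5.9% / 2.9% | 6.1% / 3.0% | 6.8% / 3.4% |
| 50,000 | 5.1% / 2.5% | 5.1% / 2.6% | 5.2% / 2.6% |

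**Step 3: when false 'higher' findings pass 5%.** This needs 1.96/√(1 + n/m) < 1.645, that is m < n / [(1.96/1.645)² − 1] = n/0.42. The limits are about 917 for n = 385, 1,100 for n = 462 and 1,834 for n = 770.

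**Step 4: check by simulation.** Binomial simulation with Wilson intervals (400,000 runs per setting; n = 385 and 770) agrees closely on the two-sided error at 14.3%, 30% and 50.5%. The 'higher' share rises somewhat as prevalence falls. At 3.3% with m = 1,000 it is 6.2% (n = 385) and 9.0% (n = 770), against 4.8% and 7.0% from the formula, so the limits in Step 3 are too low for rare conditions. With 385 participants, part of that gap belongs to the interval itself: at 3.3% the 'higher' share is 3.3% even with an effectively infinite survey.

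**Step 5: what the correction does.** An interval for the difference that uses both variances restores 5% two-sided, as far as sampling error goes. At p = 50% its half-width is 1.96 × √(0.25/n + 0.25/m). For n = 770 it rises from 3.5 points (published figure taken as constant) to 4.7 (m = 1,000) or 5.6 (m = 500). For n = 385 it rises from 5.0 to 5.9 or 6.6.

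**The case against.** **No decision rule is written.** The protocol says the intervals will be used to compare. It sets no rejection rule for Objective 2 and does not forbid use of the published sources' own intervals. Checking whether two intervals overlap would err the other way and be conservative. This stands in part: the error rates above belong to the natural reading, not to an explicit rule. But an interval set against a figure is most simply read as asking whether it excludes that figure.

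**The detail could be left to a statistical analysis plan.** One may exist and is not shown. Yet the protocol names a method here, and the named method has no place for the second variance.

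**The comparators may be large.** The 14.3% source is described in the reference list as a national sample, and the 3.3% glaucoma source as a systematic review. For such sources the excess may be small. On the other side, the 50.5% source studied patients admitted to one acute geriatric unit, and matching on age range reduces the denominator to a subgroup. The protocol does not settle the sizes.

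**The 770 column is optimistic about completion.** Expected completion is 60% for acuity, 70% for retinoscopy and 85% for ophthalmoscopy, so those figures are an upper end.

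**Methodology matters more.** Background attributes the spread from 14.3% to 50.5% mainly to study methodology. That is 36.2 points, against a study half-width of 3.5 to 5.0 points at 50% prevalence. This stands fully: adding the missing variance does not by itself make the comparison sound.

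**A stronger reading to avoid.** A reader might infer that false 'higher' findings generally exceed 5%. The documents do not support that. The nominal rate in that direction is 2.5%, and 5% is passed only for small or moderate surveys (Step 3), whose sizes are unknown.

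**Conclusion.** The point holds in a conditional form. As written, the comparison gives the published estimates no sampling error. When a difference is read off from an interval that excludes the published figure, the two-sided error is above 5% for any finite survey, and false 'higher' findings are above 2.5%. Over assumed surveys of 500 to 5,000 people, the two-sided error runs from about 22% down to 6%, depending also on how many participants are evaluable. With a survey of 50,000 it is 5.1% to 5.2%, which is of no practical consequence.

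The result rests on three assumptions: the natural reading of the sentence, survey sizes that the documents do not give, and simple binomial sampling in both sources. It concerns sampling error alone and does not show that any particular comparison will mislead. It is worth correcting because the method is fixed in the text and the change is small.

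**What to change.** Replace the comparison sentence in Data analysis with wording to this effect:

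*For each condition, the difference (or ratio) between the study prevalence and the published general-population prevalence will be reported with a 95% confidence interval that combines the standard errors of both estimates, the published one being taken from its counts or its reported interval. Any statement that prevalence is higher in people with dementia will rest on this interval. Where the source gives neither counts nor an interval, the comparison will be descriptive only. The interval reflects sampling error and does not cover differences between sources in age range, setting or definition of visual impairment.*

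The cost is a few sentences of text and extraction of counts or intervals from the published papers. No participants or measurements are added. The comparison loses some precision, as shown in Step 5, and sources without usable counts can no longer support a claim of higher prevalence.
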